12.3 Response Criteria for Patients with Solid Tumors

See the table in Section 8.0 for the schedule of tumor evaluations. In addition to the scheduled scans, a confirmatory scan should be obtained on the next consecutive cycle following initial documentation of objective response.

As outlined, patients will be assigned to one of the following categories for assessment of response: a) solid tumor (non-CNS) and measurable disease (Section 12.4); b) neuroblastoma with MIBG positive lesions (Section 12.5); c) CNS tumor (Section 12.7); and d) lymphoma/histiocytosis (Section 12.8). Note: Neuroblastoma patients who do not

have MIBG positive lesions should be assessed for response as solid tumor patients with measurable disease.

Response and progression will be evaluated in this study using the revised Response Evaluation Criteria in Solid Tumors (RECIST) guideline (version 1.1) [Eur J Ca 45:228-247, 2009]. Key points are that 5 target lesions are identified and that changes in the largest diameter (unidimensional measurement) of the tumor lesions but the shortest diameter of malignant lymph nodes are used in the RECIST v 1.1 criteria.

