- Tumor Disease Evaluation should be obtained on the next consecutive cycle after initial documentation of either a PR or CR. Subsequent scans may restart 2 cycles after the confirmatory scan. If the institutional investigator determines that the patient has progressed based on clinical or laboratory evidence, he/she may opt not to confirm this finding radiographically.
- 4-A Neurological exam also required for CNS patients.
- 4-B Non- Hodgkin Lymphoma/ Histiocytosis patients are required to have PET scans within 2 weeks prior to start of therapy and should also be followed with PET scans if positive at diagnosis. Refer to Section 12.8
- Patients with neuroblastoma must have both CT/MRI and MIBG scintigraphy prior to the start of protocol therapy if the patient was enrolled with or has a history of having MIBG avid tumor. Otherwise the patient must have either FDG-PET/CT or PET/MR prior to the start of protocol therapy. For patients with neuroblastoma and measurable disease by CT or MRI, lesions should be measured and followed using the same modality (CT or MRI) in addition to MIBG or FDG-PET/CT. For patients with neuroblastoma and evaluable disease by MIBG scintigraphy, use the same modality (MIBG scintigraphy) to image and follow patients; CT/MRI are not required but may be performed as clinically indicated. Refer to Section 12.5 and Section 12.8:
- Bone marrow aspirate and/or biopsy only required in patients suspected of having bone marrow metastasis on the basis of history, symptoms, laboratory evaluation or other clinical data.
- Bone marrow aspirate and/or biopsy should be performed only when complete response or partial response is identified in target disease or when progression in bone marrow is suspected.
- 7. The medication diary should be collected and reviewed weekly during cycle 1 (medication). The medication diary should also be reviewed after completion of each treatment cycle and uploaded into RAVE.

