10.0 CRITERIA FOR REMOVAL FROM PROTOCOL THERAPY AND OFF STUDY CRITERIA

10.1 Criteria for Removal from Protocol Therapy

- a) Clinical (including physical examination or serum tumor markers) or radiographic evidence of progressive disease (See Section 12).
- b) Adverse Events requiring removal from protocol therapy (See Section 6).
- c) Refusal of protocol therapy by patient/parent/guardian
- d) Non-compliance that in the opinion of the investigator does not allow for ongoing participation.
- e) Completion of 26 cycles of therapy.
- f) Physician determines it is not in the patient's best interest.
- g) Repeated eligibility laboratory studies (CBC with differential, bilirubin, ALT (SGPT) or serum creatinine) are outside the parameters required for eligibility prior to the start of protocol therapy (See Section 8.1).
- h) Study is terminated by Sponsor.
- i) Pregnancy
- j) Patient did not receive protocol treatment after study enrollment

Patients who are removed from protocol therapy during cycle 1 should continue to have the required observations in Section 8.1 until the originally planned end of the cycle or until all adverse events have resolved per Section 13.4.4, whichever happens LATER. The only exception is with documentation of the patient's withdrawal of consent from the APEC1621SC screening protocol. Patients who are removed from protocol therapy in subsequent cycles should have the necessary observations to ensure adequate clinical care.

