11.3 Study Design

The primary cohort and any biomarker negative expansion cohorts defined below will employ single stage A'Hern designs of N=20 and N=10 respectively. The agent will be deemed worthy of further study in the relevant subset of patients (i.e. biomarker positive in any histology, biomarker positive in a particular histology, etc) if the decision rule is met. Operating characteristics are shown below.

Cohort	N	Decision Rule	Alpha	Power
Primary biomarker positive		≥ 3 responses	10%	90%

Histology-specific biomarker positive expansion cohorts will, by definition, be deemed worthy of further study, since they will have at least 3 responses. The table below shows 90% confidence intervals (Wilson method) for a range of observable response rates.

Cohort Size Observed Response Rate		90% Confidence Interval	
10	30%	13% - 56%	
10	40%	19% - 65%	
10	50%	27% - 73%	

11.3.1 **Primary Cohort**:

APEC1621M will evaluate a primary cohort of 20 mutation-matched ("biomarker positive") evaluable patients of any histology for the primary study aim of determining the objective response rate (CR/PR according to the response criteria in Section 12.3) to the agent. Using an A'Hern design⁵³ with alpha=10%, a sample of N=20 will provide 90% power to detect an improvement in response rate from 5%, if the treatment is ineffective, to 25% if the targeted therapy is sufficiently effective to warrant further study. If there are at least 3 responses out of 20 in the primary cohort, the biomarker/therapy match will be deemed a success.

11.3.2 Histology-Specific Biomarker Positive Expansion Cohorts:

If ≥ 3 patients in the primary cohort with the same histology show signs of objective response (CR/PR according to the response criteria in Section 12.3), a histology-specific biomarker positive expansion cohort will open after the primary cohort is completed to up to 7 evaluable patients for a total sample size of 10 evaluable biomarker positive patients with that histology. This will allow us to estimate more precisely the activity in biomarker positive patients of that histology. See

We will open up to 3 such expansion cohorts for biomarker positive patients (i.e., if 3 histologies have \geq 3 responses, we will open a total of 3 expansion cohorts as described above). Note that this can only happen if the response rate in the primary cohort is at least 45% (9/20) and there cannot be more than 21 additional evaluable patients in total for these expansion cohorts.

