11.5 Evaluability for Response

Any eligible patient who is enrolled and receives at least one dose of protocol therapy will be considered evaluable for response. Any patient who receives non-protocol anti-cancer therapy during the response evaluation period will be considered a non-responder for the purposes of the statistical rule, unless they show an objective response prior to receiving the non-protocol anti-cancer therapy (in which case they will be considered a responder). Patients who demonstrate a complete or partial response confirmed by central review will be considered to have experienced a response. All other patients will be considered non-responders. Patients who are not evaluable for response evaluation may be replaced for the purposes of the statistical rule. All patients considered to have a response (CR or PR) must have imaging studies reviewed centrally at the COG. Centers will be notified by the COG about requests for scans of patients with stable disease. Preliminary assessment of activity using institutionally provided tumor measurements will be entered into CDUS quarterly. The central review by COG will be provided as the final reviewed assessment of response when such becomes available.

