12.7.4 Evaluation of organ enlargement

Complete Response (CR): Regress to normal

Partial response (PR): Spleen must have regressed by >50% in length

beyond normal

Stable Disease (SD): No increase consistent with progression

Progressive Disease (PD): In the setting of splenomegaly, the splenic length must increase by 50% of the extent of its prior increase beyond baseline. If no prior splenomegaly, must increase by at least 2 cm from baseline.

New or recurrent splenomegaly

12.8 **Best Response**

Two objective status determinations of disease status, obtained on two consecutive determinations, separated by at least a 3 week time period, are required to determine the patient's overall best response. Two objective status determinations of CR before progression are required for best response of CR. Two determinations of PR or better before progression, but not qualifying for a CR, are required for a best response of PR. Two determinations of stable/no response or better before progression, but not qualifying as CR or PR, are required for a best response of stable/no response; if the first objective status is unknown, only one such determination is required. Patients with an objective status of progression on or before the second evaluations (the first evaluation is the first radiographic evaluation after treatment has been administered) will have a best response of progressive disease. Best response is unknown if the patient does not qualify for a best response of progressive disease and if all objective statuses after the first determination and before progression are unknown.

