12.8.1 Evaluation of Best Overall Response

The best overall response is the best response recorded from the start of the treatment until disease progression/recurrence (taking as reference for progressive disease the smallest measurements recorded since the treatment started). The patient's best response assignment will depend on the achievement of both measurement and confirmation criteria.

Table 5. Sequences of overall response assessments with corresponding best response.

1st Assessment	2 nd Assessment	Best Response
Progression		Progressive disease
Stable, PR, CR	Progression	Progressive disease
Stable	Stable	Stable
Stable	PR, CR	Stable
Stable	Not done	Not RECIST classifiable
PR	PR	PR
PR	CR	PR
PR, CR	Not done	Not RECIST classifiable
CR	CR	CR

12.8.2 **Duration of Response**

Duration of overall response: The duration of overall response is measured from the time measurement criteria are met for CR or PR (whichever is first recorded) until the first date that recurrent or progressive disease is objectively documented (taking as reference for progressive disease the smallest measurements recorded since the treatment started).

The duration of overall CR is measured from the time measurement criteria are first met for CR until the first date that progressive disease is objectively documented.

Duration of stable disease: Stable disease is measured from the start of the treatment until the criteria for progression are met, taking as reference the smallest measurements recorded since the treatment started, including the baseline measurements.

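### Sections 11.5 and 12.3.1.1 credit one centrally reviewed PR/CR, while 11.4 with 12.8 needs two determinations, and no text says which rule governs the 3-of-20 decision

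*Combined protocol and SAP*

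**What the plan says.** **Decision rule.** Section 11.3.1 sets alpha at 10% and states that "a sample of N=20 will provide 90% power to detect an improvement in response rate from 5%, if the treatment is ineffective, to 25" per cent. The match is called a success on this condition: "If there are at least 3 responses out of 20 in the primary cohort". In 11.3.2, three responses within one histology open an expansion cohort.

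**Who is a responder.**
- Section 11.4 goes by best response: it must be PR or CR.
- Section 11.5 makes any eligible, enrolled patient evaluable after a single dose and counts a PR or CR upheld by central review. A patient given other anti-cancer therapy during the evaluation period is a non-responder "unless they show an objective response prior to receiving the non-protocol anti-cancer therapy (in which case they will be considered a responder"). Everyone else is a non-responder, and patients not evaluable for response may be replaced.
- Section 12.3.1.1 asks for a PR or CR upheld by central review before other anti-cancer therapy. It does not mention a repeat scan.
- Section 12.8 says "Two determinations of PR or better before progression, but not qualifying for a CR, are required for a best response of PR". CR likewise needs two, and the determinations must be at least 3 weeks apart.
- Table 5 (12.8.1) labels a first PR or CR whose second assessment was not done "Not RECIST classifiable".

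**When the second scan is taken.** Section 12.3 says "a confirmatory scan should be obtained on the next consecutive cycle following initial documentation of objective response". Section 8.1, footnote 4, agrees: "Tumor Disease Evaluation should be obtained on the next consecutive cycle after initial documentation of either a PR or CR". Section 5.1 defines a cycle as 28 days of therapy. For removal after cycle 1, Section 10.1 says only this: "Patients who are removed from protocol therapy in subsequent cycles should have the necessary observations to ensure adequate clinical care". Section 10.2 adds 30 days of follow-up, described in terms of adverse events. The central-review package in 8.2.1 consists of the baseline scans and the end-of-cycle evaluations made while on the subprotocol.

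**The concern.** The primary endpoint has two responder definitions that agree for most patients and part company for one kind: a patient with a single PR or CR, upheld centrally, and no second assessment. Nothing states which definition prevails.

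The schedule allows such patients to occur. The first on-treatment evaluation comes after two cycles, and the confirmatory scan is attached to the cycle that follows. A patient may leave therapy in between for an adverse event, refusal or a physician's decision, or may move to other treatment. The published text then requires no confirmatory scan.

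With a threshold of 3 in a single-arm, unblinded trial, the choice of rule could be made after the count is known, and one patient could decide the verdict.

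**Working it through.** **1. The sections applied to the same patient.** Both patients below are evaluable, have a PR at the end of cycle 2 that central review upholds, and have no second assessment.

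| Rule | A: stops therapy, no other treatment | B: goes on to other anti-cancer therapy |
|---|---|---|
| 11.5, read literally | Responder (upheld centrally) | Responder (response came before the other therapy) |
| 12.3.1.1, read literally | Responder | Responder |
| 11.4 with 12.8 and Table 5 | Best response is neither PR nor CR | Best response is neither PR nor CR |
| 11.5 catch-all, if 12.8 governs | Non-responder | Non-responder |
| 11.5 replacement clause | Should not apply after one dose, but the Table 5 label invites it | Same |

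In 11.5 and 12.3.1.1, confirmation refers to central review. In 12.8 it means a second determination.

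**2. The plan's own figures.** Inputs from 11.3: N = 20, success at 3 or more, null rate 5%, target rate 25%.

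P(X ≥ 3) = 1 − Σ(k = 0 to 2) C(20,k) p^k (1−p)^(20−k)

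- p = 0.25: 1 − (0.0032 + 0.0211 + 0.0669) = 0.9087, which reproduces the stated 90% power.
- p = 0.05: 1 − (0.3585 + 0.3774 + 0.1887) = 0.0755, below the 10% ceiling.

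**3. What one patient does.** If the count is 3 with the disputed patient and 2 without, the verdict flips. The chance of exactly 3 of 20 is 0.134 at a 25% rate and 0.060 at 5%. Wilson intervals, at the 90% level that 11.3 uses for the expansion cohorts:
- 3/20: 6.2% to 32.2%
- 2/20: 3.4% to 26.2%
- 2/19, if the patient is dropped: 3.6% to 27.4%

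**4. Illustration of the effect on error rates.** Let q be the share of first PR/CRs that never get a second determination. The documents give no value, so the range is an assumption.

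*Design rates are single-scan rates, but two determinations are required.* The counted rates become 0.25(1−q) and 0.05(1−q).

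| q | Power | Type I error |
|---|---|---|
| 0 | 0.909 | 0.075 |
| 5% | 0.887 | 0.067 |
| 10% | 0.861 | 0.059 |
| 20% | 0.794 | 0.044 |

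*Design rates are already confirmed rates, and two determinations are required.* Nothing changes: power 0.909, type I error 0.075.

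*Design rates are confirmed rates, but a single scan counts.* The counted null rate becomes 0.05/(1−q). Type I error is 0.085 at q = 5%, 0.097 at 10%, 0.110 at 15% and 0.126 at 20%, so it passes the 10% ceiling between q = 10% and q = 15%.

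**The case against.** The best defence is that the sections can be read together. Section 11.4 defines a responder by best response and refers to Section 12, and 12.8.1 makes best response depend on confirmation as well as measurement. On that reading, the sentences in 11.5 and 12.3.1.1 only fix the timing relative to other therapy, and patients A and B are both non-responders. This is reasonable and may be what was intended, but it is not stated, and 11.5 in its own words credits patient B. The defence therefore supports a clarification rather than removing the need for one.

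A reader might infer that a patient who stops therapy cannot be scanned and that true responders are bound to be lost. The documents do not support that. No scan is required, but none is forbidden. Imaging may be part of clinical care. The 30-day follow-up could hold either confirmation interval if the patient stops soon after the first response. Later follow-up falls under the screening protocol, which is not available here, and Section 6 is not in the published text.

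A reader might also infer that the trial's power is below 90%. That does not follow either. It needs a value of q that no document gives, and it needs 25% to be a single-scan rate. If the 25% already means confirmed response, power is unaffected.

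Finally, requiring a response to persist on treatment is a legitimate choice, and a scan after stopping also reflects drug withdrawal. That leaves the sponsor free to choose the rule, but not to leave two in place.

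**Conclusion.** The inconsistency is real and rests on no assumed figure. Read literally, 11.5 and 12.3.1.1 count a single centrally upheld PR/CR; 11.4 with 12.8 and Table 5 does not. One patient of this kind can turn 3 of 20 into 2 of 20, or the reverse, and so decide the primary conclusion.

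How often such patients will occur is unknown. The power figures (88.7%, 86.1% and 79.4% at q = 5%, 10% and 20%) are illustrative and hold only if 25% is a single-scan rate and two determinations are required. Under a confirmed 25% the figure is 90.9%.

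The rule should be settled before the responder count is known. The cycle-based timing of the confirmatory scan is a secondary weakness: it creates the opening for the disputed case, but does not by itself show that responders will be lost.

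**What to change.** **Responder rule (main change).**
- State one rule across 11.4, 11.5, 12.3.1.1 and 12.8. One way is to make the exception for other anti-cancer therapy in 11.5 depend on having met the 12.8 criteria for a best response of PR or CR, and to add the same reference to 12.3.1.1.
- State that an evaluable patient with an unconfirmed PR/CR counts as a non-responder in the 3-of-20 rule and is not replaced.

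**Confirmatory scan (secondary change).**
- In 8.1 footnote 4 and 12.3, time the scan by calendar interval from first documentation, whether or not another cycle is given and, where feasible, before other anti-cancer therapy. Carry this into 10.1 and 10.2.
- Reconcile the interval: Table 1 in 12.4.3 gives at least 28 days, and 12.8 at least 3 weeks.
- Add the scan to the central-review package in 8.2.1, including when it is taken off therapy.

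**Cost.** Amendment wording, plus a return visit for one scan in a few off-therapy patients; it is the same confirmatory scan the protocol already asks of responders. The real trade-off is that a single unconfirmed PR followed by other therapy, which 11.5 now credits on its face, would no longer count.

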12.3.1 Definitions

12.3.1.1 Evaluable for objective response:

Eligible patients who receive at least one dose of protocol therapy will be considered evaluable for response. Evaluable patients who demonstrate a complete or partial response confirmed by central review before receiving non-protocol anti-cancer therapy will be considered a responder. All other evaluable patients will be considered non-responders

12.3.1.2 Evaluable Non-Target Disease Response:

Eligible patients who have lesions present at baseline that are evaluable but do not meet the definitions of measurable disease and have received at least one dose of protocol therapy will be considered evaluable for non-target disease response. The response assessment is based on the presence, absence, or unequivocal progression of the lesions.

12.3.2 Disease Parameters

12.3.2.1 Measurable disease: Measurable lesions are defined as those that can be accurately measured in at least one dimension (longest diameter to be recorded) as ≥ 20 mm by chest x-ray, as ≥ 10 mm with CT scan, or ≥ 10 mm with calipers by clinical exam. All tumor measurements must be recorded in millimeters (or decimal fractions of centimeters).

Note: Tumor lesions that are situated in a previously irradiated area might or might not be considered measurable. If the investigator thinks it appropriate to include them, the conditions under which such lesions should be considered must be defined in the protocol.

- 12.3.2.2 Malignant lymph nodes: To be considered pathologically enlarged and measurable, a lymph node must be ≥ 15 mm in short axis when assessed by CT scan (CT scan slice thickness no greater than 5 mm). At baseline and in follow-up, only the short axis will be measured and followed.
- 12.3.2.3 Non-measurable disease: All other lesions (or sites of disease), including small lesions (longest diameter < 10 mm or pathological lymph nodes with ≥ 10 to < 15 mm short axis), are considered non-measurable disease. Bone lesions, leptomeningeal disease, ascites,

pleural/pericardial effusions, lymphangitis cutis/pulmonitis, inflammatory breast disease, and abdominal masses (not followed by CT or MRI), are considered as non-measurable.

Note: Cystic lesions that meet the criteria for radiographically defined simple cysts should not be considered as malignant lesions (neither measurable nor non-measurable) since they are, by definition, simple cysts. 'Cystic lesions' thought to represent cystic metastases can be considered as measurable lesions, if they meet the definition of measurability described above. However, if non-cystic lesions are present in the same patient, these are preferred for selection as target lesions.

- 12.3.2.4 Target lesions: All measurable lesions up to a maximum of 2 lesions per organ and 5 lesions in total, representative of all involved organs, should be identified as target lesions and recorded and measured at baseline. Target lesions should be selected on the basis of their size (lesions with the longest diameter), be representative of all involved organs, but in addition should be those that lend themselves to reproducible repeated measurements. It may be the case that, on occasion, the largest lesion does not lend itself to reproducible measurement in which circumstance the next largest lesion that can be measured reproducibly should be selected. A sum of the diameters (longest for non-nodal lesions, short axis for nodal lesions) for all target lesions will be calculated and reported as the baseline sum diameters. If lymph nodes are to be included in the sum, then only the short axis is added into the sum. The baseline sum diameters will be used as reference to further characterize any objective tumor regression in the measurable dimension of the disease.
- 12.3.2.5 Non-target lesions: All other lesions (or sites of disease) including any measurable lesions over and above the 5 target lesions should be identified as non-target lesions and should also be recorded at baseline. Measurements of these lesions are not required, but the presence, absence, or in rare cases unequivocal progression of each should be noted throughout follow-up.

